© 2018 Boehringer Ingelheim International GmbH or one or more of its affiliated companies. All rights reserved.

This document may not - in full or in part - be passed on, reproduced, published or otherwise used without prior written permission.

| | |
|--|--|
| Number of global amendment | 4 |
| Date of CTP revision | 26 Nov 2018 |
| EudraCT number | 2014-004896-22 |
| BI Trial number | 1351.1 |
| BI Investigational Product(s) | BI 863909 |
| Title of protocol | An open label, phase I, dose escalation study to characterize the safety, tolerability, pharmacokinetics, and pharmacodynamics of intravenous doses of BI 836909 in relapsed and/or refractory multiple myeloma patients |
| To be implemented only after approval of the IRB/IEC/Competent Authorities | X |
| To be implemented immediately in order to eliminate hazard – IRB / IEC / Competent Authority to be notified of change with request for approval |  |
| Can be implemented without IRB/IEC/ Competent Authority approval as changes involve logistical or administrative aspects only |  |
| Sections to be changed | 
 1. Titel page 2. Flow Chart, Section 3.1, Section 6.2.5.3 3. Section 2.3 4. Section 4.1.4.1.4 5. Section 4.2.1.2.3 6. Appendix 10.1 |

Proprietary confidential information.

© 2018 Boehringer Ingelheim International GmbH or one or more of its affiliated companies. All rights reserved.

This document may not - in full or in part - be passed on, reproduced, published or otherwise used without prior written permission.

| | |
|-----------------------------------|--|
| Number of global amendment | 4 |
| Description of change | 
1. The following on the Titel page: Trial Clinical Monitor Was changed to Clinical Trial Leader2. FlowChart, Section 3.1 Overall trial design and plan, Section 6.2.5.3 Extended follow up Wording was introduced to allow for extended follow up for responders: In case of ongoing clinical benefit, patients can be followed up to collect data for duration of response. Follow-up visits for responders will be at 3, 6 and 12 months after EOT if a patient did not progress, started a new anti-cancer treatment, died, or withdrew informed consent and will assess related SAEs and AESIs.3. 2.3 Benefit-Risk Assessment The following was added: Cytokine release can be associated with clinical symptoms such as fever, chills, nausea, vomiting, hypotension, dyspnoea, tachypnea, headache, tachycardia, rash, and/or hypoxia.4. 4.1.4.1.4 Handling of infusion-related reactions or cytokine release syndromes Recommendations for CRS management were modified and Table 4.1.4.1.4: 1 Grading and management of cytokine release syndrome was added.5. 4.2.1.2.3 Infections The following was added: Prophylactic antibiotics, antifungal and antivirals are allowed and should be given according to institutional standards. Pneumocystis prophylaxis should also be given according to institutional standards. For patients who are considered to have an increased risk for herpes infections, the prophylaxis is mandatory unless medically contraindicated. Subjects who may experience neutropenia for 7 days or longer are at a high risk for infectious complications. As appropriate, these subjects will be administered prophylactic antibacterial, antifungal, and antiviral medications. These subjects will be monitored for early signs of breakthrough infections after the initiation of antibacterial therapy to prompt additional evaluation and |

Proprietary confidential information.

© 2018 Boehringer Ingelheim International GmbH or one or more of its affiliated companies. All rights reserved.

This document may not - in full or in part - be passed on, reproduced, published or otherwise used without prior written permission.

| | |
|--|--|
| 
Number of global amendment
 | 
4
 |
| | 
possible therapy modification.
 
Infections should be treated according to local guidelines/standards.
 
Patients who develop fever >38.3°C or a sustained temperature of >38°C ≥1 h will be hospitalised, undergo the following diagnostic work-up and started on empirical treatment with broad spectrum i.v. antibiotics according to institutional standards:
 
 - Blood cultures from central line and peripheral veins - Urine culture - CT-Thorax low dose - Respiratory virus by pharyngeal wash (Parainfluenza 1-4, Influenza A + B, Adenovirus, Metapneumovirus, Echovirus, Rhinovirus, Bocavirus, Coronavirus, Entovirus und RSV by multiplex PCR) 
Subjects with active systemic infections requiring IV antibiotics, antivirals, or antifungals should not be dosed with BI 836909 until infection has resolved and if being treated with an anti-infectious therapy, the course of such therapy should have been completed.
 
Patients requiring interruption of treatment for >14 days due to active infection will be permanently discontinued.
 
6. 10.1 International Myeloma Working Group (IMWG) uniform response criteria for multiple myeloma The following was added: SD – Not meeting criteria for CR, VGPR, PR, or progressive disease
 |
| 
Rationale for change
 | 
 1. Change in nomenclature 2. Collection of data for long-term responders 3. Request of the French authority ANSM to add additional clinical signs and symptoms as described in CTCAE v5 in order to enhance investigators' awareness for occurrence of CRS clinical events. However, the grading of CRS will continue to be based on CTCAE v4 until completion of the trial. 4. Request of the French authority ANSM to add risk minimization measures and detailed procedures in case of suspicion of CRS. 5. Correction/completion of IMWG criteria. |

Proprietary confidential information.

© 2018 Boehringer Ingelheim International GmbH or one or more of its affiliated companies. All rights reserved.

This document may not - in full or in part - be passed on, reproduced, published or otherwise used without prior written permission.

APPROVAL / SIGNATURE PAGE
Document Number: c02587386
Technical Version Number:5.0
Document Name: clinical-trial-protocol-revision-04

2. LIST OF ABBREVIATIONS

Include a list of all abbreviations used in the tSAP

Term	Definition / description
ADA	Anti-drug antibody
AE	Adverse event
AESI	Adverse event of special interest
ALT	Alanine aminotransferase
AST	Aspartate aminotransferase
BCMA	B-cell maturation antigen
BI	Boehringer Ingelheim
BRPM	Blinded Report Planning Meeting
CR	Complete response
CRS	Cytokine release syndrome
CTC	Common Terminology Criteria
CTP	Clinical Trial Protocol
CTR	Clinical Trial Report
DLT	Dose limiting toxicity
DM&SM	Boehringer Ingelheim Data Management and Statistics Manual
DOR	Duration of response
ECG	Electrocardiography
ECOG	Eastern Cooperative Oncology Group
ICH	International Conference on Harmonisation
IgA	Immunoglobulin A
IgG	Immunoglobulin G
IgM	Immunoglobulin M
IMWG	International Myeloma Working Group
i.v.	intravenous
MedDRA	Medical Dictionary for Regulatory Activities
MQRM	Medical Quality Review Meeting
MRD	Minimal residual disease
MTD	Maximum tolerated dose
PD	Progressive disease

Term	Definition / description
PFS	Progression free survival
PK	Pharmacokinetics
PR	Partial response
PT	Preferred term
PD	Protocol deviation
Q1	Lower quartile
Q3	Upper quartile
RPM	Report planning meeting
SC	Safety committee
sCR	Stringent complete response
SOC	System organ class
TSAP	Trial statistical analysis plan
VGPR	Very good partial response

[figure not shown]
3. INTRODUCTION

As per ICH E9 [1], the purpose of this document is to provide a more technical and detailed elaboration of the principal features of the analysis described in the protocol, and to include detailed procedures for executing the statistical analysis of the primary and secondary variables and other data.

This TSAP assumes familiarity with the Clinical Trial Protocol (CTP), including Protocol Amendments. In particular, the TSAP is based on the planned analysis specification as written in CTP Section 7 “Statistical Methods and Determination of Sample Size”. Therefore, TSAP readers may consult the CTP for more background information on the study, e.g., on study objectives, study design and population, treatments, definition of measurements and variables, planning of sample size, randomization.

SAS[®] Version 9.4 or newer version will be used for all analyses.

4. CHANGES IN THE PLANNED ANALYSIS OF THE STUDY

5. ENDPOINTS

5.1 PRIMARY ENDPOINTS

The primary objective is to assess the safety of BI 836909 in humans and to determine the maximum tolerated dose (MTD). The primary endpoints are the following:

- MTD of BI 836909: MTD is defined as the highest dose of the dose level tested where ≤ 1 patient out of 6 develops dose limiting toxicity (DLT)
- Number of patients with DLTs

5.2 SECONDARY ENDPOINTS

5.2.1 Key secondary endpoint

[figure not shown]
This section is not applicable as no key secondary endpoints have been specified in the protocol.

[figure not shown]
5.2.2 Secondary endpoints

- Objective response rate (percentage of patients with stringent complete response (sCR), complete response (CR), partial response (PR) and very good partial response (VGPR))
- Duration of response (DOR)
- Minimal residual disease (MRD)
- Duration of MRD response
- Progression-free survival (PFS)

Secondary pharmacokinetic endpoint is:

- Serum concentration at steady state (C_{ss}) for c.i.v.

6. GENERAL ANALYSIS DEFINITIONS

6.1 TREATMENTS

Patients are administered BI 836909 as a continuous 4-week infusion followed by a 2-week break for 5 cycles or until progression, unacceptable adverse events or other reason necessitating withdrawal. In case of ongoing clinical benefit a maximum of 5 additional treatment cycles can be given.

[figure not shown]

Figure 6.1:1 Overall study design

For all analyses, statistics will be tabulated by treatment dose group (see [Table 6.1: 1](#)).

Table 6.1: 1 Treatment labels for use in the CTR

Treatment label	Short label
BI 836909, 0.2 µg/d, c.i.v. ^[1]	0.2 µg/d civ
BI 836909, 0.4 µg/d, c.i.v. ^[1]	0.4 µg/d civ
BI 836909, 0.8 µg/d, c.i.v. ^[1]	0.8 µg/d civ
BI 836909, 1.6 µg/d, c.i.v. ^[1]	1.6 µg/d civ
BI 836909, 3.2 µg/d, c.i.v.	3.2 µg/d civ
BI 836909, 6.5 µg/d, c.i.v.	6.5 µg/d civ
BI 836909, 13 µg/d, c.i.v.	13 µg/d civ
BI 836909, 25 µg/d, c.i.v.	25 µg/d civ
BI 836909, 50 µg/d, c.i.v.	50 µg/d civ
BI 836909, 100 µg/d, c.i.v.	100 µg/d civ
BI 836909, 200 µg/d, c.i.v.	200 µg/d civ
BI 836909, 400 µg/d, c.i.v.	400 µg/d civ
BI 836909, 800 µg/d, c.i.v. ^[2]	800 µg/d civ

[1] The 1st four treatment label (0.2 – 1.6 µg/d) may be combined into one column for selected displays.

[2] Further doses will be tested in case that MTD could not be confirmed at a dose level of 800 µg/day. Intermediate doses cohorts will be entered if determined by the safety committee, for example, in case that the dose cohort 400 µg/day exceeds MTD (>1 patients out of 6 with DLT) and no DLT is observed on 200 µg/day, 300 µg/day might be considered.

The purpose of the definition below is to describe the different study interval in this trial.

The treatment periods of the study are:

- Screening period:
The screening period starts from the date of informed consent and ends at the date of the first administration of study drug.
- Treatment period:

Treatment period starts from the date of the first administration of study drug and ends at the date of the last administration of study drug.

- Residual effect period:

Residual effect period starts from the date of the last administration of study drug + 1, and ends at the date of the last administration of study drug + 30 days .

- Follow-up period;

The Follow-up period starts from the last administration of study drug + 30 days.

Please see [Table 6.1:2](#) below, for a definition of treatment periods. The purpose of the definitions below is to describe the treatment periods in this trial.

Table 6.1: 2 Definition of treatment periods

Analyzing Treatment Period	Start Date	Start Time	End Date
Screening	Date of informed consent		Date of the first administration of BI 836909
Treatment	Date of the first administration of BI 836909	Time of the first administration of BI 836909	Date of the last administration of BI 836909
Residual effect period	Date of the last administration of BI 836909 + 1 day		Date of the last administration of BI 836909 + 30 day
Post-treatment	Date of the last administration of BI 836909 + 31 day		Not applicable

For safety analyses, adverse events (AEs) will be classified to one of the following time periods: “Screening”, “Treatment”, or “Post-treatment”. Section 5.2.2 of the protocol specifies that all AE reported within 30 days of the last trial medication will be considered on treatment. Detailed rule for assigning AEs to these time periods are listed below:

- If the date of informed consent \leq AE onset date $<$ date of first administration of BI 836909, then the AE is assigned to “Screening”;
- If date of first administration of BI 836909 \leq AE onset date \leq date of last administration of BI 836909 + 30 days, then the AE is assigned to “Treatment”;
- If AE onset date $>$ date of last administration of BI 836909 + 30 days, then the AE is assigned to “Post-treatment”.

6.2 IMPORTANT PROTOCOL DEVIATIONS

A protocol deviation (PD) is important if it affects the rights or safety of the study patients, or if it can potentially influence the primary outcome measurements in a non-negligible way. Patients with important PDs that could potentially impact the evaluation of the primary endpoints will be excluded (Refer to [Section 6.3 Table 6.3:1](#)).

A list of important PDs is given in [Table 6.2: 1](#) below. Important PDs will be reviewed at Medical Quality Review Meetings (MQRMs) conducted periodically during the trial. A list of protocol deviations will be discussed at the Blinded Report Planning Meeting (BRPM).

If the data show other important PDs, this table will be supplemented accordingly at MQRMs or RPMs or through team review of the manual PD log. The decision whether a patient will be excluded from the analysis will be made at the final BRPM prior to DBL.

Table 6.2: 1 Important protocol deviations

Category / Code	Description	Requirements	Excluded from
A	Entrance criteria not met		
A1	Inclusion criteria not met		
A1.1	Disease severity for MM not met	Inclusion criteria (IN) 1 or 3 not met.	None
A1.2	Disease measurability not met	IN 2	None
A1.3	Requirements on ECOG status, age, ability to adhere to study visit schedule not met	IN 5 or 6 not met	None
A2	Exclusion criteria met		
A2.1	Certain prior or current disease conditions.	Exclusion criteria (EX) 1, 2, 3, 23, 24 or 25 met	None
A2.2	Last anticancer or investigational treatment, transplantation	EX 4, 6, 7 or 21 met	None
A2.3	Pregnancy / breast feeding / contraception related	EX 17, 18 or 19 met	None
A2.4	Clinical relevant concurrent medical disease, infections or conditions	EX 9, 10, 11, 12, 13,14, 15 or 16 met	None
A2.5	Hypersensitivity to investigational drug	EX 22 met	None
B	Informed consent		
B1	Informed consent not available/not done	Informed consent date missing	All
B2	Informed consent too late	Informed consent date was after Screening Visit date	None
B3	Outdated informed consent signed	e.g., Outdated version of informed consent with major change	None
C	Trial medication and randomisation		
C1	Incorrect trial medication taken	Medication kit assigned not matching IVRS assignment	None

Table 6.2: 1 (continued) Important protocol deviations

Category / Code	Description	Requirements	Excluded from
C2	Non-compliance with BI 836909	Any patients with non-compliance issues as defined in Section 5.4.2 or other issue related such as manipulation of bump by patients.	None
C3	Improper preparation or administration of BI 836909 for IV infusion	Create listing, decision at MQRM / RPM, see CTP Section 4.1.4 for drug preparations and mandatory pre-medications. Check comment in the eCRF.	None
D	Concomitant medication		
D2	Prohibited medication use concomitantly with study medication	
 • Chronic oral use of NSAIDs • Chronic systemic use of corticosteroids • Quinidine • Cytotoxic/myelosuppressive , immunologic drugs or radiation therapy 	None
F	Other category		
F1	Other trial specific	Other protocol deviations deemed to be IPD from manual PD log, e.g., multiple procedures not performed correctly.	None

Note: Missing visits, evaluations, and tests will be considered missing data, not protocol deviations. All final decisions as to whether any deviation is relevant will be taken at the RPM.

6.3 SUBJECT SETS ANALYSED

All entered subjects who received trial medication will be included in the safety analysis and in the pharmacokinetic analysis set depending on the availability of measurement values and on their adherence to the CTP. The criteria for inclusion into these populations are defined as follows:

Populations: Please see below for the specified populations.

Treated set (TS): all patients who were administered study medication. This set of patients is used for all analyses except for analysis of PK data.

[figure not shown]
MTD evaluation set (MTDS): all patients in the TS who were not replaced for the MTD determination. Rules for replacement of patients were defined in CTP, Section 4.1.4.5. In addition safety committee will decide the replacement of patients.

PK Analysis Set (PKS): all evaluable patients in the treated set which provide at least one evaluable observation for at least one PK endpoint.

The TS will be used for all efficacy and safety analyses. In addition, the MTDS represent the populated used for MTD determination. The primary analyses of DLTs during 1st cycle will be based upon the MTDS. PK analyses will be based on the PKS. Refer to Protocol Section 7.3.5 on handling PK endpoints.

Table 6.3: 1 Subject sets analysed

Class of endpoint	Treated set	Subject set	
		MTDS	PKS
Primary and key secondary endpoints	X	primary analysis	
Other secondary and further endpoints	X		
Safety endpoints	X		
Demographic/baseline endpoints	X		
PK endpoints			X

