All trial relevant documentation will be stored in BIRDS. Trial relevant documentation which has to be at the trial site will be filed in the ISF at the investigator site. The ISF document will be kept in print-out version at the sites as far as required by local regulation and BI-SOP.

A safety committee (SC) of the investigators in cooperation with the responsible trial monitor and the medical project leader of the sponsor as well as medical representatives from Amgen will be implemented to analyse ongoing safety information and decide on further steps in dose finding. Prior to escalating the dose to the next higher dose cohort there will be a safety teleconference or meeting between trial investigators and the medical project leader of the sponsor to discuss any findings in the ongoing and already recruited cohorts, this means that all available clinical and safety data including repeated cycles of prior dose cohorts will be taken into consideration for assessments and decision making. Participation of the coordinating investigator or [REDACTED] deputy is a mandatory requirement for this committee to establish a quorum. After the defined observation period of each cohort this safety committee will discuss the need to enter additional patients or dose cohorts or release the next dose cohort and dose increment as per protocol. The same is true for the decision to switch from single patient cohorts to the 3+3 design. Step dosing may be implemented based on cytokine release syndrome qualifying for DLT following the following guidance:

- Restart with previous dose level for 4 days (one bag) and then escalate to current dose level until the end of the cycle.

The composition of the SC will be documented in BIRDS. The tasks and responsibilities will be agreed in contracts between the SC members and the Sponsor. SC will decide on the switch from single patient cohorts to the 3+3 design independently from defined dose cohorts based on clinical activity (antitumor response) and/or clinically relevant safety or pharmacodynamics findings.

Data Management and Statistical Evaluation will be done by BI according to BI SOPs.

Tasks and functions assigned in order to organise, manage, and evaluate the trial will be defined according to BI SOPs. A list of responsible persons and relevant local information can be found in the ISF.

Summary of assessments (see corresponding [Flow charts](#)):

Proprietary confidential information.

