5.2.1.1 Dose limiting toxicity

Dose limiting toxicity (DLT) is defined as any drug-related non-haematological adverse event CTCAE version 4.03 grade 3 or higher. The following grade 3 events will not be considered

Proprietary confidential information.

© 2018 Boehringer Ingelheim International GmbH or one or more of its affiliated companies. All rights reserved.

This document may not - in full or in part - be passed on, reproduced, published or otherwise used without prior written permission.

DLT: febrile neutropenia and infection responding to antibiotic/anti-infective treatment within 48 hours, fatigue, headache, insomnia, fever, hypotension.

Laboratory parameters of grade ≥ 3 but not considered clinically relevant and/or responding to routine medical management, will not be considered dose limiting toxicities.

Additional events that are considered DLT include:

- Persistent grade 4 neutropenia or thrombocytopenia until day 56 in the absence of detectable Multiple Myeloma as it may reflect a marrow toxic effect of BI 836909.

If infusion related reactions (IRR) or cytokine release syndromes (CRS) \geq grade 2 occur or constitute DLT events the safety committee may decide to switch to step dosing for the respective and any higher dose cohort. In that case the infusion will be started at 10(-30)% of the target dose on day 1 of the course and will be escalated to the full target dose from day 9 of course 1 on for the remainder of the course. Patients will be hospitalized and pre-medicated for the dose increase the same way they are for start of treatment. Once the safety committee decides to switch to step dosing patients that may have developed DLT due to IRR or CRS events may be replaced at the respective cohort by additional patients who will receive treatment with the adapted administration schedule (step dosing).

Although hematological adverse events (e.g. anemia, thrombocytopenia, neutropenia, lymphopenia) will not be considered DLT, complications resulting from hematological events, e.g. bleeding due to thrombocytopenia or grade 4 infection due to neutropenia are classified as non-hematological adverse events and are covered by the above definition of DLT. Nevertheless, hematological adverse events will be considered for definition of the dose for further development.

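### If the step-dosing replacement option in protocol 5.2.1.1 is used, the primary cycle 1 DLT count in SAP 6.3 drops the replaced DLT patients and mixes flat and step schedules under one dose label

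*SAP*

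**What the plan says.** SAP 5.1 and protocol 3.1 define the MTD as the highest dose level tested with at most one DLT in six patients. Protocol 3.2 says the MTD is exceeded once at least two of up to six patients at a dose level have a DLT.

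SAP 6.3 defines the "MTD evaluation set (MTDS): all patients in the TS who were not replaced for the MTD determination" and states that "The primary analyses of DLTs during 1st cycle will be based upon the MTDS". For replacement it refers to protocol 4.1.4.5 and adds: "In addition safety committee will decide the replacement of patients". No criteria are attached. Protocol 4.1.4.5 replaces patients who discontinue permanently for reasons other than DLT, and it keeps patients with a DLT evaluable for the primary analysis.

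Protocol 5.2.1.1 provides another route, which SAP 6.3 does not cite. Once the committee switches to step dosing, "patients that may have developed DLT due to IRR or CRS events may be replaced at the respective cohort by additional patients", and those additional patients receive the step schedule. The switch applies to the cohort concerned and to any higher one.

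SAP 6.1 tabulates by dose group, and Table 6.1:1 has no step-dosing label. SAP 7 keeps patients in their assigned dose cohort, and SAP 7.4 displays cycle 1 DLTs by dose level.

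**The concern.** Read together, these texts make membership of the primary analysis set depend on the primary outcome. A flat-dosed patient with a CRS DLT can be removed by replacement. A flat-dosed patient without a DLT stays, unless the committee chooses to replace that patient too. The replacement patient receives a different schedule but is counted under the same dose label.

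The primary table could then show a dose as meeting the MTD rule without showing which schedule was tolerated, or in how many patients. The primary endpoint of a first-in-human trial should not leave that open. The situation was foreseen: protocol 2.3 expects that cytokine release may occur, and protocol 3.1.1, 4.1.4.5 and 5.2.1.1 all provide for step dosing.

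**Working it through.** The plan gives no DLT rate, power or other figure for this point, so there is nothing to reproduce.

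**Step 1: worked cohort, no rate assumed.** Six patients are dosed flat and two have a CRS DLT. Both are replaced one for one by step-dosed patients without DLT.

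| Count | Patients included | DLTs |
|---|---|---|
| MTDS, SAP 6.3 as written | 4 flat without DLT + 2 step | 0/6 |
| Treated set | 6 flat + 2 step | 2/8 |
| Flat schedule | 6 flat | 2/6 |
| Step schedule | 2 step | 0/2 |

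The MTDS figure meets the rule of at most one DLT in six. The flat figure exceeds the MTD under protocol 3.2. The step figure has too few patients for the rule to classify. With the same two DLTs among only three flat-dosed patients, the MTDS is 0/3 and the treated set 2/5; 0/3 alone would not establish an MTD defined on six.

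**Step 2: what the zero counts support.** The exact one-sided 95% upper limit for 0/n is 1 − 0.05^(1/n). For 0/6 it is 1 − 0.05^(1/6) = 39%. For the two patients who actually received the step schedule it is 1 − 0.05^(1/2) = 78%. Protocol 3.1 allows up to 6 further patients at the MTD or recommended dose. If all six received the step schedule without DLT, 0/8 would give 1 − 0.05^(1/8) = 31%.

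**Step 3: direction, under assumptions that are not in the documents.** Let p be the flat-dose DLT risk, s the share of DLTs that are CRS/IRR, and f the fraction of the CRS/IRR risk left under step dosing. The step-dose risk is q = p·s·f + p(1 − s). Assume standard 3+3 staging, replacement of all CRS/IRR DLT patients once two or more DLTs occur, and no committee override. After a switch at three patients, 0/3 passes and 1/3 adds three step-dosed patients; after a switch at six, at most one remaining DLT passes.

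The chance that a cohort on one schedule with risk r passes is (1 − r)³ + 3r(1 − r)⁵. All-flat at p = 0.33: 0.67³ + 3 × 0.33 × 0.67⁵ = 0.301 + 0.134 = 0.434. All-step at s = 1, f = 0.5, so q = 0.165: 0.835³ + 3 × 0.165 × 0.835⁵ = 0.582 + 0.201 = 0.783. Exact enumeration at p = 0.33, f = 0.5:

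| CRS/IRR share s | 25% | 50% | 75% | 100% |
|---|---|---|---|---|
| MTDS passes, all cohorts | 0.54 | 0.67 | 0.82 | 0.95 |
| All-step cohort passes | 0.52 | 0.61 | 0.70 | 0.78 |
| MTDS passes, given the option is used | 0.38 | 0.53 | 0.71 | 0.90 |
| MTDS DLTs exceed flat DLTs, given use | 0.05 | 0.04 | 0.02 | 0.01 |

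Across all cohorts the MTDS excess over an all-step cohort is 0.02 to 0.16. It is 0.03 to 0.09 at p = 0.20 and −0.01 to 0.20 at p = 0.50. If step dosing brings no benefit (f = 1), the all-flat chance of 0.43 rises to 0.53, 0.63, 0.73 and 0.84 in the MTDS. Given that the option is used, the MTDS is less favourable than an all-step cohort at shares of 25% and 50%, about equal at 75%, and more favourable at 100%.

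At the moment of one-for-one replacement the count cannot exceed the flat-dosed count. Later additions can raise it: 2/3 flat, both replaced and one step-dosed DLT, gives 1/3; three more step-dosed patients, all with DLT, give 4/6.

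**The case against.** The strongest reply is that the exclusion is intended. Protocol 5.2.1.1 expressly authorises replacing IRR/CRS DLT patients when the regimen changes, and SAP 6.3 says that replaced patients leave the MTDS. Patients dosed flat tell little about the new regimen. That defends testing the new schedule, but not the mixed count: by the same logic flat-dosed patients without DLT should not inform the step result either, and the text leaves them in.

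The mitigation is real. "The TS will be used for all efficacy and safety analyses", so the replaced patients' events stay in the DLT tables for all courses and in the tables of grade 3 or higher IRR and CRS (SAP 7.8.1). Table 6.3:1 also marks the treated set for primary endpoints, and protocol 7.3 names only the treated set. The committee makes the dose decisions, and "all available clinical and safety data including repeated cycles of prior dose cohorts will be taken into consideration". But the SAP labels the MTDS as primary, and none of these tables is split by schedule.

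The scope is also narrow. Three things must happen: an IRR/CRS event, a committee switch and a decision to replace. By this route mixing affects the cohort in which the switch occurs, because higher cohorts start step-dosed.

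A reader might infer a one-way bias towards declaring the dose tolerable, or that the count can only fall. Neither is supported: the direction against a fully step-dosed cohort depends on assumed rates, and the trigger of two DLTs in the calculation is not in the documents, since protocol 5.2.1.1 permits a switch after any IRR/CRS of grade 2 or higher. Nor do the documents show that the option was used or that toxicity would be hidden.

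**Conclusion.** The point holds as a conditional defect in the primary DLT count and should be fixed; confidence is medium. If the protocol 5.2.1.1 option is used, following SAP 6.3 as written can turn 2/6 flat-dosed DLTs into 0/6 in the primary analysis. That figure is not a valid DLT count for the flat schedule or for the step schedule. This conclusion rests on the texts and the worked counts, not on any assumed rate. The 3+3 probabilities are illustrations only and do not establish a direction of bias relative to a fully step-dosed cohort.

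A related protocol matter widens the possible mixture. Protocol 5.2.1.1 says that "the infusion will be started at 10(-30)% of the target dose on day 1 of the course", with the full target from day 9, and protocol 4.1.4.5 is similar. Protocol 3.1.1 instead says: "Restart with previous dose level for 4 days (one bag) and then escalate to current dose level until the end of the cycle". The latter might be read as re-challenge of an affected patient, but the text does not settle this.

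Some SAP and protocol text and figures are not visible, so silence is judged on the visible text only.

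**What to change.** In SAP 6.3, cite protocol 5.2.1.1 beside 4.1.4.5. In SAP Table 6.1:1 and 7.4, show cycle 1 DLTs by dose and schedule actually received (flat or step), for both the MTDS and the treated set. Show each replaced DLT patient under the dose and schedule received. List every replaced patient with the reason and the schedule. These are descriptive displays and do not decide who counts toward the MTD.

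The sponsor must reconcile two matters. One is protocol 3.2, protocol 5.2.1.1 and SAP 6.3 on who counts toward the rule of at most one in six after a switch. The other is the differing step-dosing descriptions in protocol 3.1.1 and in 4.1.4.5/5.2.1.1. No MTD rule, dose or schedule is proposed here.

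The cost is SAP wording, one schedule column and one listing. The downside is that a step-dosed result may visibly rest on few patients and the DLT rate may look less favourable. The reconciliation may touch the protocol, because SAP wording alone cannot settle it.
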